1.3.3. Cutaneous Sensitization, Irritancy Potential and Tolerability

1.3.3.1. Local Tolerability in Sensitive Skin Areas

In a study of healthy subjects (16 men and 16 women) who applied crisaborole ointment 2% or vehicle for 21 days to sensitive area application sites (including extensor areas, intertriginous areas, genitals, and face/hairline), 99% of assessments of local tolerability were graded as 0 (none), with an overall maximum grade of 2 (moderate) and only 0.1% of

assessments graded higher than 1 (mild) (Study AN2728-PSR-107). There were no marked differences in burning/stinging, erythema, or pruritus at any of the application sites over the course of the study between subjects who received crisaborole ointment 2% or Vehicle. Overall, crisaborole ointment 2% was well tolerated over 21 days of dosing in sensitive skin areas of healthy subjects.

1.3.3.2. Sensitizing and Cumulative Irritation Potential

In a repeat-insult patch test and cumulative irritation study in healthy subjects (Study AN2728-RIPT-101), the potential for inducing cutaneous sensitization was assessed in 238 subjects randomized in Cohort 1. None of the subjects demonstrated cutaneous evidence of sensitization potential (a reaction of at least Grade 4 [definite edema] or a pattern suggestive of contact sensitization in the opinion of the Investigator) to the investigational products, crisaborole ointment 2% or vehicle. The potential for causing cutaneous irritation was evaluated among 40 subjects randomized in Cohort 2. There were no statistically significant differences in irritation between the crisaborole ointment 2% and vehicle. Crisaborole ointment 2% and vehicle showed no evidence of sensitization and only very minimal irritation.

1.3.4. Clinical Experience

Seven (7) clinical trials of topical formulations of crisaborole have been completed to date in subjects with AD. Key study information is summarized below.

- In a multicenter, maximal use, systemic exposure (MUSE) study in 34 pediatric subjects ranging in age from 2 to 17 years with mild-to-moderate AD who applied crisaborole ointment 2% BID,³⁶ subjects had overall blood levels of crisaborole that were low and similar to those previously observed in adults after adjusting for [REDACTED]. Absorption across the skin was rapid, with a median T_{max} of 3.0 hours on both Day 1 and Day 8.
- In a 4-week, single arm, open-label safety, tolerability and [REDACTED] trial in adolescents with mild-to-moderate AD involving [REDACTED],³⁷ disease severity improved over the 28-day treatment period.
- In a 6-week bilateral comparison trial of subjects with mild-to-moderate AD,³⁸ 68% of AD lesions treated with crisaborole ointment 2% BID showed greater improvement in atopic dermatitis severity index (ADSI) than vehicle-treated lesions (20%) at 4 weeks (primary endpoint). These response rates were similar at Day 14 and Day 42 (end of treatment).
- In a 4-week bilateral comparison trial of 86 adolescent subjects with mild-to-moderate AD,³⁹ crisaborole ointment 2% BID showed greater improvement than the lower concentration of crisaborole ointment, 0.5% applied BID for 29 days, and was more efficacious than either concentration applied once daily (QD).

- In two Phase 3 multicenter, randomized, double-blind, vehicle controlled studies in subjects ≥ 2 years of age and older with AD, crisaborole ointment 2% outperformed the vehicle in the primary efficacy analysis, proportion of subjects achieving success in [REDACTED] at Day 29. [REDACTED]
- An additional Phase 3 multicenter, open-label, long-term extension study (AN2728-AD-303) of crisaborole ointment 2% for the treatment of mild to moderate AD in adults and children as young as 2 years of age evaluated the long-term safety of topical crisaborole. No clinically important safety signals were identified by this study.⁴²

Crisaborole has been well tolerated across completed clinical studies. No clinically important safety signals have been identified, including during a Phase 3 multicenter, open-label, long-term extension study of crisaborole ointment 2% for mild to moderate AD in adults and children as young as 2 years of age. Most AEs have been mild, and most considered unrelated or unlikely to be related to investigational product. The most common drug-related AEs have been application site reactions.

Refer to the IB for further information on the clinical experience with crisaborole ointment 2%.²²

1.4. Rationale

1.4.1. Study and Dose Rationale

This 4-week safety study will evaluate the safety profile of crisaborole ointment 2% BID in subjects who are 3 months to less than 24 months of age with mild-to-moderate AD. In addition, [REDACTED] will be assessed in a subgroup of at least 16 subjects under maximal use conditions, defined as systemic exposure conditions related to a high percent of body surface area involvement which would maximize the potential for drug absorption with anticipated clinical use of crisaborole. While crisaborole has been studied extensively in patients and healthy volunteers 24 months of age and older, it has not been tested in patients less than 2 years of age. As such, the current study is being conducted as a post-approval commitment to FDA as part of the pediatric study plan.

The dose strength and regimen selected for this study has been shown to be safe, well tolerated and efficacious in patients and healthy volunteers 2 years of age and older who participated in previously conducted studies of crisaborole. Crisaborole ointment 2% applied BID was studied in two Phase 3, randomized, double-blind, vehicle-controlled studies, and a Phase 3 open-label long-term safety study. Data from the two controlled studies showed a statistically significant therapeutic effect compared to vehicle with no safety concerns in patients 2 years and older. In the open-label study, crisaborole ointment 2% applied BID,

demonstrated that the long-term use was well tolerated and not associated with any systemic safety signals. The Phase 1 maximal use absorption study in children and adolescents aged 2 to 17 years old,³⁶ showed that subjects who were administered crisaborole ointment 2% BID (single dose on Days 1 and 8) to [REDACTED] had overall blood levels of crisaborole that were similar to those previously observed in adults after [REDACTED]. An analysis of variance (ANOVA) showed no statistically significant differences in CC parameters between the age cohorts represented in the study (Cohort 1, ages 12–17 years; Cohort 2, ages 6–11 years; and Cohort 3, ages 2–5 years).

Based on the results of clinical studies conducted with crisaborole ointment 2% to date, it is anticipated that crisaborole ointment 2% will demonstrate similar efficacy and satisfactory safety and local tolerability in the pediatric population to be enrolled in this study.

1.4.2. Single Reference Safety Document

Additional information for crisaborole may be found in the Single Reference Safety Document (SRSD), which for this study is the current version of the crisaborole Investigator’s Brochure.

2. STUDY OBJECTIVES AND ENDPOINTS

| Primary Objective | Primary Endpoint(s) |
|--|---|
| To study the safety of crisaborole ointment 2% applied twice daily (BID) in children aged 3 months to less than 24 months with mild to moderate AD | Incidence of treatment emergent AEs (including application site reactions), SAEs, and clinically significant changes in height, weight, vital signs, ECG and clinical laboratory parameters |
| [REDACTED] | [REDACTED] |
| [REDACTED] | [REDACTED] |
| [REDACTED] | [REDACTED] |
| [REDACTED] | [REDACTED] |
| [REDACTED] | [REDACTED] |
| [REDACTED] | [REDACTED] |
| [REDACTED] | [REDACTED] |
| [REDACTED] | [REDACTED] |
| [REDACTED] | [REDACTED] |
| [REDACTED] | [REDACTED] |
| [REDACTED] | [REDACTED] |
| [REDACTED] | [REDACTED] |
| [REDACTED] | [REDACTED] |
| [REDACTED] | [REDACTED] |
| [REDACTED] | [REDACTED] |
| [REDACTED] | [REDACTED] |
| [REDACTED] | [REDACTED] |
| [REDACTED] | [REDACTED] |

| | |
|--|-----|
| | CCI |
|--|-----|

Abbreviations: AD=atopic dermatitis; AE=adverse event; BID=twice a day; SAE=serious adverse event;

CCI; ECG=electrocardiogram; EOT=end of treatment; CCI
Cmax =maximum observed plasma concentration; Tmax = time to maximum
observed plasma concentration; AUC(0–12)=area under the plasma concentration-time curve from
0 to 12 hours post dosing.

3. STUDY DESIGN

3.1. Study Overview

This is a Phase 4, multicenter, open label, safety study to evaluate the safety of crisaborole ointment 2% in children aged 3 months to less than 24 months with AD. CCI

Approximately 125 subjects will be enrolled. Subjects will be between 3 months (at the time of the Screening visit) to less than 24 months of age at the time of Baseline/Day 1 with mild-to-moderate AD involving assessed on Baseline/Day 1.

In addition, a cohort of at least 16 of the 125 subjects will be included in a subgroup for assessment. These subjects must have moderate AD and a minimum of 35% treatable %BSA, excluding the scalp, and must complete all assessments to be included in the analysis. Of these subjects, at least 3 subjects who are less than 9 months of age will be enrolled. Subjects discontinuing for reasons other than TEAE may be replaced at the discretion of the sponsor to ensure 16 subjects complete the assessments. Only selected study sites will participate in the assessment.

Written informed consent will be obtained from the parent(s)/legal guardian prior to any study procedures.

Scheduled study visits/telephone contacts for all subjects will occur at Screening (up to 28 days prior to Baseline/Day 1), Baseline/Day 1, Day 8, Day 15, Day 22, Day 29 (end of treatment/early termination), Day 36, and Day 57 (end of study).

Days 22 and 36 will be conducted through a telephone contact with the subject's parent(s)/legal guardian to assess the subject's condition, and whether any AEs, including application site reactions, have occurred since the last visit. Investigational product compliance, lifestyle requirements (Day 22 only) and concomitant medications will also be reviewed. The parent(s)/legal guardian will be contacted by site staff on Day 57

(approximately 28 days after the last dose application) for a follow-up telephone conversation (end of study) during which site staff will assess the subject's condition and whether any AEs, including application site reactions, have occurred since the last visit.

In addition, subjects in the [REDACTED] cohort will have twice daily visits on Days 2 through 7 for application of investigational product at the site, as well as 3 [REDACTED] sample collections from prior to AM dose until 12 hours post dose on Day 8. If desired, the protocol allows for a visiting health care professional to assist with twice daily dosing in the subject's home for some or all of the dose applications during the [REDACTED] portion of the study and any 2 of the 3 [REDACTED] sample collections. Further information on home-based dose application and [REDACTED] sample collection for the [REDACTED] cohort is provided in [Sections 5.8.2](#) and [Section 7.3.1](#), respectively.

For the approximately 16 subjects in the [REDACTED] cohort, 3 additional blood samples of approximately 1 mL each (approximately 3 mL total) will be collected for plasma crisaborole and metabolites PK analysis, according to the following schedule:

- Before the Day 8 AM dose (ie, 168 hours \pm 1 hour after recorded time of completion of the Day 1 dose application);
- 3 hours \pm 20 minutes after recorded time of completion of the Day 8 AM dose application;
- 12 hours \pm 1 hour after recorded time of completion of the Day 8 AM dose application.

Selection criteria for the study population are described in [Section 4](#). Detailed information about the investigational product treatment regimen is provided in [Section 5.8](#). Detailed information about study procedures and assessments is provided in [Section 6](#) and [Section 7](#).

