| To study the safety of crisaborole ointment 2% applied twice daily (BID) in children aged 3 months to less than 24 months with mild to moderate AD | Incidence of treatment emergent AEs (including application site reactions), SAEs, and clinically significant changes in height, weight, vital signs, ECG and clinical laboratory parameters |

| | |
|--|--|
| | 
[REDACTED]
 
[REDACTED]
 
[REDACTED]
 
[REDACTED]
 
CCI
 
[REDACTED]
 |
|--|--|

Abbreviations: AD=atopic dermatitis; AE=adverse event; BID=twice a day; [REDACTED]; ECG=electrocardiogram; EOT=end of treatment; [REDACTED]; SAE=serious adverse event; [REDACTED]; t_{1/2}; CCI; C_{max}=maximum observed plasma concentration; AUC₍₀₋₁₂₎=area under the plasma concentration-time curve from 0 to 12 hours post dosing; T_{max}=time to reach maximum observed plasma concentration

Study Design:

This is a Phase 4, multicenter, open-label safety study to evaluate the safety of crisaborole ointment 2% in approximately 125 subjects who are 3 months to less than 24 months of age, with mild-to-moderate AD involving at least 5% treatable [REDACTED]. In addition, a cohort of at least 16 of the 125 subjects enrolled will be included in a subgroup for CCI assessment. These subjects must have moderate AD with a minimum of [REDACTED], excluding the scalp, and must complete all CCI assessments to be included in the CCI analysis. Of these subjects, at least 3 subjects who are less than 9 months of age will be enrolled.

Approximately 30 investigational sites will participate in this study. Only selected study sites will participate in the CCI assessment.

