9.1. Sample Size Determination

This is a multi-center, open-label, safety study of subjects with AD. To ensure 100 completers, 125 subjects will be enrolled assuming a 20% drop out rate. Of the 125 subjects enrolled, at least 16 subjects with moderate AD and [REDACTED] [REDACTED] excluding scalp, who have completed all [REDACTED] assessments will be included in a subgroup for [REDACTED] assessment. The sample size was determined by clinical judgment based on

Sponsor experience with other clinical studies with the investigational product and was not based on statistical power.

CCI

within a SOC or a preferred term by using the event with the greatest relationship and highest severity within each classification.

Serious adverse events (SAEs) will be summarized by SOC and PT, and individual SAEs will be listed by subject. A list of subjects who prematurely discontinue from the study due to an AE will be provided.

Clinically significant changes in height, weight, vital signs, ECG and safety laboratory parameters will be summarized.

[REDACTED]

CCI
[REDACTED]

[REDACTED]

[REDACTED]

[REDACTED]

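### Followed as written, the completers-only rule for the Day 8 sampling cohort drops valid concentrations from any infant who misses one draw

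*Protocol*

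**What the plan says.** Protocol section 3.1 describes the cohort as a floor: "a cohort of at least 16 of the 125 subjects will be included in a subgroup". These subjects "must complete all assessments to be included in the analysis". The Protocol Summary, under Study Design, carries the same condition with some words blacked out: "must complete all CCI assessments to be included in the CCI analysis".

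Section 9.1 counts the 16 in the same way: "Of the 125 subjects enrolled, at least 16 subjects with moderate AD and" a further condition that is partly blacked out, "excluding scalp, who have completed all" of the cohort's assessments. The sampling paragraph of section 3.1 is looser: "For the approximately 16 subjects in the" cohort, three extra samples are taken on Day 8 (before the morning dose, at 3 hours and at 12 hours).

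On replacement, section 3.1 says: "Subjects discontinuing for reasons other than TEAE may be replaced at the discretion of the sponsor", with the aim that 16 complete. Section 6.12 repeats that sentence for the cohort. Immediately before it stands a general sentence that lets the investigator, after consulting the sponsor, replace any withdrawn subject. The general sentence makes no exception for adverse events.

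SAP section 4.3 puts everyone who receives at least one dose in the safety analysis set. The SAP text between sections 4.3 and 4.5 is blacked out, as is the end of the missing-data sentence in SAP section 5.3.

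**The concern.** The visible rule decides who enters the analysis, and not only who counts toward 16. The three samples do different jobs. The abbreviations under the objectives table in Protocol section 2 include Cmax, Tmax and AUC(0–12). A 12-hour sample is needed for AUC(0–12). It is not needed to report the pre-dose or 3-hour concentration, and section 1.3.4 gives a median Tmax of 3.0 hours in the earlier maximal-use study of children aged 2 to 17 years. An all-or-nothing rule can therefore discard the value nearest the expected peak because a later draw failed.

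Failed draws are foreseeable in this age group. The Schedule of Activities footnote on screening blood draws allows for an upset child or collection problems, and section 7 accepts that some tests will prove unfeasible. An infant who misses a draw but stays on study has not discontinued or withdrawn, so neither replacement sentence applies.

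The cohort is meant to describe exposure when absorption is at its highest, in about 16 infants, with at least 3 under 9 months to be enrolled. At that size each excluded profile is noticeable, and the visible text gives no check on whether the excluded infants differ from the rest.

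**Working it through.** **The plan's own figure.** The only derived size is the overall enrolment in section 9.1: 100 completers with 20% dropout gives 100 / (1 − 0.20) = 125, which matches. The cohort figure of 16 has no stated derivation, and section 9.1 says the sample size rests on clinical judgment and not on power.

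**What the rule costs in data.** Inputs: three samples per infant (section 3.1), and a success probability p per draw. The documents do not give p. I assume 0.95 and 0.90, with independent draws. I also take the assessments that must be complete to be the three samples; if others are included, the loss is larger.

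- Share of sampled infants with all three samples = p³.
- Share of valid concentrations set aside: a valid sample is kept only if the other two also exist, so the share lost is 1 − p².

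| | p = 0.95 | p = 0.90 |
|---|---|---|
| All three samples, p³ | 0.857 | 0.729 |
| Complete profiles expected from 16 sampled, 16p³ | 13.7 | 11.7 |
| Valid samples expected from 48 draws, 48p | 45.6 | 43.2 |
| Valid samples used under the rule, 48p³ | 41.2 | 35.0 |
| Share of valid samples set aside, 1 − p² | 9.75% | 19% |

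**Does the target of 16 fail?** Suppose exactly 16 entered and no loss was made up. The chance that all 16 complete is (1 − q)¹⁶, where q is the assumed loss per subject. Suppose instead that 20 entered; the chance of at least 16 completers is then an exact binomial tail.

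| Loss per subject, q | All 16 of 16 | At least 16 of 20 |
|---|---|---|
| 1% | 85% | >99% |
| 2% | 72% | >99% |
| 5% | 44% | >99% |
| 10% | 19% | 96% |
| 20% | 2.8% | 63% |

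The left column applies only if enrolment stops at 16. Sections 3.1 and 9.1 say at least 16, and section 9.1 counts completers, so the text lets the cohort grow until 16 are complete. With no replacement, the entry that gives at least a 90% chance of 16 completers is 17 at 1% or 2% loss, 18 at 5%, 20 at 10% and 23 at 20%.

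**What enlarging the cohort does not cure.** It restores the count. It does not bring back the partial profiles, and the set is still chosen on completion.

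**The case against.** Several objections have force.

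- *The target.* A reader might infer that the 16 completers are not assured. The documents do not support that: 16 is a floor with no cap, and section 9.1 counts those who complete. What remains is that no mechanism for going beyond 16 is spelled out, and that the sampling paragraph says approximately 16.
- *Replacement.* A reader might infer that infants lost to an adverse event cannot be replaced. The cohort sentence leaves them out, but the general sentence in section 6.12 covers any withdrawn subject. The two need reconciling; a ban is not established.
- *Bias.* A reader might infer that the infants with the highest exposure are the ones removed. Nothing in the documents links failed draws or early withdrawal to exposure, so the direction is unknown.
- *Redaction.* The words naming the assessments and the analysis are blacked out, and so is any SAP set for this cohort. Partial profiles may already be listed or summarised by time point. Protocol section 9 also lets the SAP modify the protocol, and requires an amendment only for major changes to the primary endpoints or their analyses. This objection stands as a limit on certainty. It does not alter the sentence that sites and readers can see.
- *Benefit.* Without the 12-hour value, AUC(0–12) is not directly supported. The gain lies mainly in concentrations by time point, and possibly in Cmax.
- *Weight.* This is a descriptive analysis outside the primary endpoint, which is safety, and everyone dosed stays in the safety set.

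**Conclusion.** The point holds for the inclusion rule. As printed, the protocol excludes an infant from the sampling analysis for one missing Day 8 assessment, which discards usable concentrations and selects the set on completion. The size is not known from the documents. With independent draws that succeed with probability 0.95 (0.90), 14% (27%) of sampled infants would be excluded and about 10% (19%) of valid concentrations would go unused. Those rates are assumptions and serve only to show scale.

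The primary safety analysis is untouched, and the target of at least 16 completers remains attainable. How partial profiles will finally be handled cannot be confirmed, because the relevant SAP text may be among what is blacked out. The change is worth making because using all available concentrations is the better method and costs very little.

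**What to change.** 1. Replace the inclusion sentence in Protocol section 3.1 and the Protocol Summary. Every dosed cohort subject with at least one evaluable concentration enters the summary by time point, and enters each derived parameter that the available samples support. AUC(0–12) is derived only where the 12-hour sample exists.
2. Keep completion of all assessments for two purposes: counting toward the 16, and a sensitivity set reported beside the main summary.
3. List concentrations and sampling times for subjects who left because of a TEAE after giving at least one sample. A subject who left before Day 8 has no Day 8 profile to recover.
4. If the blacked-out SAP text already defines the set this way, align the protocol sentence with it.
5. Reconcile the general and cohort-specific replacement sentences in section 6.12, and settle on one of at least 16 and approximately 16.

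The cost is wording and one extra table. The number of subjects will differ slightly between parameters, so each summary should show its own n. No added subjects or blood draws are needed.

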3.2. Number of Sites

Approximately 30 investigational sites will participate in this study. Only selected study sites will participate in the [REDACTED] assessment.

3.3. Duration of Study

Subjects will be screened for the study no more than 28 days before the initial day of dosing (Baseline/Day 1), and will receive investigational product for approximately 28 days. The study will comprise the following study periods:

- Screening Period: maximum duration of 28 days;
- Investigational Product Application Period: approximately 28 days (until Day 29 visit);

- Post-Treatment Follow-up Period: approximately 28 days. The follow-up period includes a telephone contact 7 days after the last application of investigational product and a telephone contact 28 (+3 days) days after the last application of investigational product.

The total duration of a subject's participation in the study will range from a minimum of 59 days to a maximum of 88 days, depending on the length of a given subject's screening period.

